## **Objective**

Androgenetic alopecia (AGA) is a progressive condition with limited optimal therapeutic options. While platelet-rich plasma (PRP) therapy has been explored, the apheresis technique offers a distinct method of PRP preparation that yields higher platelet purity and more consistent cellular composition compared to conventional centrifugation methods. This study is specifically designed to evaluate the clinical effectiveness of this autologous apheresis PRP and identify key predictors.

## **Design**

Given the exploratory nature of this investigation aimed at generating preliminary efficacy and safety data for a specific PRP preparation method, a single-arm design was chosen. This single-arm trial enrolled 201 male AGA patients receiving 3-5 sessions of autologous apheresis PRP injections. The primary endpoint, change in the BASP classification, was assessed by independent, blinded physicians. Patient-reported outcomes were assessed one month after treatment completion using a four-item questionnaire covering hair quality, hair thickness, hair loss reduction, and overall satisfaction. Associations between treatment response and key variables, including age, number of sessions, baseline severity, and PRP cellular composition were analyzed.

## **Methods**

### **Participants**

Eligible participants were required to meet all of the following criteria: (1) Male aged 18-55, who had history of hair loss more than 6 months and was diagnosed with AGA based on Chinese guideline for diagnosis and treatment of AGA. (2) General health: in good health with a body weight  $\geq 50$  kg, no history of hypertension, diabetes, platelet dysfunction, or any other contraindication to PRP apheresis. (3) Treatment naivety: no use of finasteride, minoxidil, or any other treatment for hair loss within

the 6 months preceding enrollment. Additionally, participants must have had no recent use of glucocorticoids (topical to treatment site for 1 month; systemic for 2 weeks) or nonsteroidal anti-inflammatory drugs (within 48 hours) prior to PRP apheresis. (4)

Laboratory parameters: blood tests within 2 weeks before PRP apheresis meeting the following criteria: hemoglobin concentration > 120 g/L, hematocrit 0.30-0.50, platelet counts > 110 × 10^9/L. No clinically significant abnormalities in inflammation, coagulation, or electrolyte panels.

Exclusion criteria: (1) Concurrent Hair Loss Treatments: Concurrent use of finasteride, minoxidil, and other hair growth treatments during PRP treatments. (2) Incomplete treatment protocol: failure to complete a minimum of 3 consecutive PRP treatment sessions as per the study protocol, or failure to complete follow-up for any reason.

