### **Interventions, Blinding, and Randomization**

Before each PRP injection, photographs of the scalp were taken from four angles (frontal, vertex, and bilateral sides) for every participant. All participants received 3 or more consecutive injections of autologous PRP into the scalp, with an interval of 3 to 5 weeks between each treatment. To ensure objective assessment, all photographs were anonymized by removing any time or sequence identifiers. Subsequently, these photographs were randomly assigned to 2 or 3 independent, blinded physicians for the assessment of hair loss severity. The physicians were blinded to the treatment stage (before- or after-treatment), patient identity, and PRP cellular composition throughout the grading process.

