## **Treatment Protocol**

Autologous PRP was prepared using a closed-system blood cell separator (NGL XCF 3000, Nigale Biomedical, China) with disposable blood cell collection consumables, following the manufacturer's standardized protocol. Approximately 20–50 mL of PRP was harvested per session, of which 2 mL was used for quality control and the remainder was aseptically aliquoted into five sterile bags and stored at –80°C. Cellular components were quantified using an automated hematology analyzer (760CS, Mindray, China). Prior to injection, the treatment area was cleansed with sterile gauze. Topical anesthesia was achieved by applying compound lidocaine cream. Subsequently, the scalp was disinfected with 75% medical-grade alcohol. Frozen PRP aliquots were thawed to room temperature immediately before use. Using a 30-gauge sterile needle, rewarmed autologous PRP was administered via intradermal and subcutaneous injections at multiple points across the treatment area, with an injection volume of 0.05 mL per point at intervals of approximately 0.5 cm. Following the procedure, the scalp was cleansed and disinfected again. Participants were advised not to wash hair for the first 48 hours after treatment. In the event of minor bleeding or fibrin deposition at injection sites, gentle cleansing with sterile gauze was recommended.

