## **Assessment Criteria**

The severity of hair loss was graded using the Basic and Specific (BASP) classification criteria. Briefly, mild cases included patterns M1, M2, C1, V1, or F1; moderate cases included M3, C2, V2, V3, F2, or F3; severe cases were defined as C3

or any U-type pattern. Coexistence of basic and specific types resulted in an upgrade to the next severity level. Based on grading by blinded, independent physicians using standardized photographs, a positive response was defined as an improvement of at least one grade in either the Basic or Specific component of the BASP system from Baseline to the day of the last treatment. When the physician-assessed gradings were inconsistent, disagreements were resolved by a third blinded assessor, with the final outcome determined by a majority decision.

Patient-reported outcomes were assessed via telephone or outpatient visit one month after treatment completion using a four-item questionnaire covering hair quality, hair thickness, hair loss reduction, and overall satisfaction. Responses are recorded on a 3-point scale: -1 (deteriorated/dissatisfied), 0 (unchanged/neutral), +1 (improved/satisfied). The outcome will be reported as the proportion of participants reporting an improvement (score of +1) for each individual item. Adverse reactions during the treatment process were recorded.

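### Exclusion criterion (2) is known only after enrolment, so the single-arm results are conditional on completion, with bias of unknown size and direction

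*Protocol*

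**What the plan says.** The Participants section has two exclusion criteria.

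- Criterion (2) removes men for "failure to complete a minimum of 3 consecutive PRP treatment sessions as per the study protocol, or failure to complete follow-up for any reason".
- Criterion (1) is "Concurrent use of finasteride, minoxidil, and other hair growth treatments during PRP treatments". Use of such treatments in the six months before enrolment is covered separately, by inclusion criterion (3).

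The rest of the Protocol agrees with criterion (2). Design states: "This single-arm trial enrolled 201 male AGA patients receiving 3-5 sessions of autologous apheresis PRP injections". Interventions, Blinding, and Randomization adds: "All participants received 3 or more consecutive injections of autologous PRP into the scalp".

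Three details bear on who could be removed and what is known about them.

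- In Treatment Protocol, after apheresis "the remainder was aseptically aliquoted into five sterile bags and stored", so a man can leave with PRP collected but not yet injected.
- "Before each PRP injection, photographs of the scalp were taken from four angles".
- In Assessment Criteria, response is an improvement of at least one grade in either "component of the BASP system from Baseline to the day of the last treatment". The only later contact described is the questionnaire one month after treatment ends.

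The Objective is to evaluate clinical effectiveness. Design presents the study as exploratory and single-arm, intended to give preliminary efficacy and safety data.

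**The concern.** Eligibility should be decided on what is known when a man enters. Criterion (2) depends on what happens afterwards, so a man can be treated and then cease to be a participant. Criterion (1) does the same only where another hair-loss treatment starts during the PRP course.

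In a one-arm study the response proportion is itself the efficacy result. Removing men who stopped because they saw no benefit would raise it. Removing men who stopped because they were already satisfied would lower it. The patient-reported proportions are conditional in the same way. So is the adverse-reaction rate: a man who stopped after one or two sessions because of a reaction would leave the count, although safety is part of the stated purpose.

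The primary outcome is fixed on the last treatment day. If follow-up in criterion (2) includes the one-month questionnaire, a man who missed only that contact could be dropped even though his primary outcome was already gradable.

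**Working it through.** The Protocol gives no response rate, number of starters or number removed, so there is no figure to reproduce. What follows shows what the rule could do. Only n=201 comes from the document; the other inputs are assumptions.

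**Inputs.** p = response rate among the 201; d = fraction of treated men removed; r = response rate among removed men.

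**All-treated rate** = p(1−d) + r·d. Men removed = 201·d/(1−d).

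With p = 0.60:

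| d | Men removed (about) | None respond (r=0) | Half rate (r=0.30) | Same rate (r=0.60) | All respond (r=1) |
|---|---|---|---|---|---|
| 5% | 11 | 57% | 58.5% | 60% | 62% |
| 10% | 22 | 54% | 57% | 60% | 64% |
| 20% | 50 | 48% | 54% | 60% | 68% |
| 30% | 86 | 42% | 51% | 60% | 72% |

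The gap between the two extreme columns is [p(1−d) + d] − p(1−d) = d, whatever p is. The 201-man rate always lies between the extremes, so the arithmetic allows bias either way.

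**Comparison with sampling error.** The 95% half-width is 1.96·√(0.60·0.40/201) = 0.0677, or 6.8 points. The downward shift is p·d if none respond and (p/2)·d at half the rate. It equals the half-width at:

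- none respond: d = 0.0677/0.60 = 11%;
- half rate: d = 0.0677/0.30 = 23%.

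For p = 0.40 (half-width again 0.0677) these thresholds are 0.0677/0.40 = 17% and 0.0677/0.20 = 34%. For p = 0.80 (half-width 0.0553) they are 0.0553/0.80 = 7% and 0.0553/0.40 = 14%. The upward shift is (1−p)·d. With p = 0.60 it reaches the half-width only at d = 0.0677/0.40 = 17%, with every removed man responding.

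At 5% removed and p = 0.60 the largest downward shift is 0.60·0.05 = 3 points, below sampling error.

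**What can be observed on removed men.** Photographs precede each injection, and response runs from baseline to the last treatment day. A one-session man's two photographs therefore fall on the same day, and no change can be seen. A two-session man has a post-baseline photograph, reflecting one injection. The first outcome is missing by construction; the second is observed.

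**The case against.** The strongest reply is that the selection is disclosed. The exclusion rule is printed, and two other sections say that the men had three or more sessions, so a careful reader can see to whom the rate applies. The study also describes itself in these terms: "Given the exploratory nature of this investigation aimed at generating preliminary efficacy and safety data". No effect has been shown, since nothing in the document says that any man was removed, and at low removal the possible shift is below sampling error. All of this stands and limits the weight of the point. It does not remove it: the 201 are described as enrolled, the result is not called a completer result, and without the number who started a reader cannot tell whether the bias is nil or large.

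Four stronger readings are tempting and not supported.

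- *The response rate is inflated.* The document gives no reasons for stopping, so no direction can be claimed.
- *Both exclusion criteria are purely post-enrolment.* Criterion (1) could also be applied at screening, to men using or planning another treatment. Criterion (2) carries the point alone.
- *Men who miss only the questionnaire are dropped.* Follow-up is not defined in the criterion, so this is a possible consequence and not a stated one.
- *No SAP could bring these men back.* The SAP is not shown and could define an all-treated set if records exist. What can be said is that the Protocol's wording takes them out of the study population.

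It would also be wrong to correct this by counting every early stopper as a failure in the primary rate. A one-session man would fail by construction, which replaces a bias of unknown direction with an imputed downward one.

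**Conclusion.** The point holds as a fault of design, accounting and labelling, and it should be fixed. Criterion (2), applied as written, makes the response proportion, the patient-reported proportions and the adverse-reaction rate conditional on completion, for a study whose aim is clinical effectiveness. This follows from the text alone and does not depend on what an SAP may contain.

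The size is not established. The illustrations rest on assumed completer rates of 40% to 80% and assumed removal of 5% to 30%. Within them, the possible shift runs from negligible to larger than the sampling error. Which applies depends on a count that the sponsor may hold and the Protocol does not give.

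**What to change.** The 201 men have already been selected, so their selection should be stated and not rewritten.

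1. Treat these items as post-enrolment events instead of eligibility criteria. Leave the restriction on concurrent treatment unchanged.
2. Report how many men had apheresis, how many had at least one injection, how many were removed, and why. Count men removed for another hair-loss treatment separately.
3. Report the response rate over all men with at least one injection beside the 201-man rate, and label the latter, with its patient-reported proportions, a completer result. Use the observed last-treatment-day grade wherever a post-baseline photograph exists, including for two-session men and men who miss only the one-month contact.
4. For men with no post-baseline photograph, including one-session men, give a range from none responding to all responding. Do not impute a single value.
5. Report adverse reactions over all men with at least one injection, and reactions to apheresis over all men who had apheresis.
6. Run the session-trend, logistic and ROC analyses on observed outcomes only, and state the selection.

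Item 6 guards against an artefact of imputation; it is not evidence against this trial. Suppose 67 men each had 3, 4 and 5 sessions, with 40 responders in each group. The linear-trend statistic, (N−1) times the squared correlation of sessions with response, is 0 (p=1.0). Adding 11 one-session and 11 two-session men, all coded as non-responders, gives N=223, a statistic of 13.3 and p=0.0003.

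If records of removed men were not kept, report the number who started and the range, and label the result a completer analysis.

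The cost is text changes, a count of starters with reasons, and retrieval of removed men's photographs and safety records where they exist. The headline rate may be less favourable.

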### **Interventions, Blinding, and Randomization**

Before each PRP injection, photographs of the scalp were taken from four angles (frontal, vertex, and bilateral sides) for every participant. All participants received 3 or more consecutive injections of autologous PRP into the scalp, with an interval of 3 to 5 weeks between each treatment. To ensure objective assessment, all photographs were anonymized by removing any time or sequence identifiers. Subsequently, these photographs were randomly assigned to 2 or 3 independent, blinded physicians for the assessment of hair loss severity. The physicians were blinded to the treatment stage (before- or after-treatment), patient identity, and PRP cellular composition throughout the grading process.

## **Treatment Protocol**

Autologous PRP was prepared using a closed-system blood cell separator (NGL XCF 3000, Nigale Biomedical, China) with disposable blood cell collection consumables, following the manufacturer's standardized protocol. Approximately 20–50 mL of PRP was harvested per session, of which 2 mL was used for quality control and the remainder was aseptically aliquoted into five sterile bags and stored at –80°C. Cellular components were quantified using an automated hematology analyzer (760CS, Mindray, China). Prior to injection, the treatment area was cleansed with sterile gauze. Topical anesthesia was achieved by applying compound lidocaine cream. Subsequently, the scalp was disinfected with 75% medical-grade alcohol. Frozen PRP aliquots were thawed to room temperature immediately before use. Using a 30-gauge sterile needle, rewarmed autologous PRP was administered via intradermal and subcutaneous injections at multiple points across the treatment area, with an injection volume of 0.05 mL per point at intervals of approximately 0.5 cm. Following the procedure, the scalp was cleansed and disinfected again. Participants were advised not to wash hair for the first 48 hours after treatment. In the event of minor bleeding or fibrin deposition at injection sites, gentle cleansing with sterile gauze was recommended.

## **Assessment Criteria**

The severity of hair loss was graded using the Basic and Specific (BASP) classification criteria. Briefly, mild cases included patterns M1, M2, C1, V1, or F1; moderate cases included M3, C2, V2, V3, F2, or F3; severe cases were defined as C3

or any U-type pattern. Coexistence of basic and specific types resulted in an upgrade to the next severity level. Based on grading by blinded, independent physicians using standardized photographs, a positive response was defined as an improvement of at least one grade in either the Basic or Specific component of the BASP system from Baseline to the day of the last treatment. When the physician-assessed gradings were inconsistent, disagreements were resolved by a third blinded assessor, with the final outcome determined by a majority decision.

Patient-reported outcomes were assessed via telephone or outpatient visit one month after treatment completion using a four-item questionnaire covering hair quality, hair thickness, hair loss reduction, and overall satisfaction. Responses are recorded on a 3-point scale: -1 (deteriorated/dissatisfied), 0 (unchanged/neutral), +1 (improved/satisfied). The outcome will be reported as the proportion of participants reporting an improvement (score of +1) for each individual item. Adverse reactions during the treatment process were recorded.

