### **Statistical Analysis**

Statistical analysis was performed using SPSS 26.0 and Prism 9.0 software. Continuous variables were tested for normality (Shapiro-Wilk test) and were presented as mean  $\pm$  SD or median (IQR), as appropriate. Categorical variables were expressed as n (%). Binary Logistic Regression Analysis was used to analyze the relationship between the effectiveness of PRP injection treatments and age, treatment sessions, initial severity at diagnosis, and cellular components in PRP. A crosstabulation analysis was conducted to assess the association between treatment

sessions and clinical effectiveness. Chi-square test was used to analyze the impact of treatment sessions on effectiveness, and Mantel-Haenszel Chi-square test was used to assess for a linear trend. Receiver Operating Characteristic (ROC) curve analysis was conducted to assess the predictive utility of PRP RBC concentrations for treatment failure (defined as 'no improvement'). A two-sided p-value of  $< 0.05$  was considered as statistical significance.

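### The severity predictor cannot separate extent of hair loss from the number of components that can improve

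*Protocol*

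**What the plan says.** Two rules stand side by side in the protocol's Assessment Criteria section.

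- **Severity.** A single pattern sets the level: "mild cases included patterns M1, M2, C1, V1, or F1"; a middle list is moderate; and "severe cases were defined as C3" or any U pattern. Then comes the upgrade: "Coexistence of basic and specific types resulted in an upgrade to the next severity level".
- **Response.** A responder shows "improvement of at least one grade in either the Basic or Specific component of the BASP system" between baseline and the last treatment day.

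The Statistical Analysis section relates response, by binary logistic regression, to "age, treatment sessions, initial severity at diagnosis, and cellular components in PRP". No term for coexisting types is named. The Assessment Criteria scale is the only definition of severity in the protocol. Predictors are part of the stated aim, which is to "evaluate the clinical effectiveness of this autologous apheresis PRP and identify key predictors", and the Design section names baseline severity among the key variables.

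**The concern.** One attribute, having both a Basic and a Specific type, enters both sides of the regression. It moves a man up the severity scale, and it gives him a second component whose improvement makes him a responder. The mild group contains only men with one route to response, while the moderate and severe groups can contain men with two.

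An association between severity and response could therefore reflect how advanced the loss is, how many components are open to improvement, or both. The planned model has nothing to tell these apart. At stake is how one predictor is read. The proportion of responders does not use the severity label and is untouched, and the point makes no claim about age, sessions or cellular composition.

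**Working it through.** The protocol gives no response rate, severity distribution or correlation between components, so there is no stated figure to reproduce. The first step follows from the text. The others are illustrations over assumed inputs.

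**1. What the rules imply.** The lowest level before upgrade is mild, so any man with both types is at least moderate after it. Now take M, C and U as Basic (7 entries, counting U once) and V and F as Specific (6 entries), and upgrade from the higher of the two levels, capped at severe. These readings are assumptions.

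- Mild: 5 single patterns, 0 pairings.
- Moderate: 6 single patterns and 3 × 2 = 6 pairings (mild with mild).
- Severe: 2 single patterns (C3, U) and 7 × 6 − 6 = 36 pairings.

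These count patterns, not patients.

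**2. Effect of a second route.** Let each component improve with probability q at every level, with correlation φ between components. One-type response is q. Both-type response is 2q − [q² + φq(1 − q)]. At q = 0.30:

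- φ = 0: 0.60 − 0.09 = 51.0%, odds ratio against one-type 2.43
- φ = 0.3: 0.60 − (0.09 + 0.063) = 44.7%, odds ratio 1.89
- φ = 0.6: 0.60 − (0.09 + 0.126) = 38.4%, odds ratio 1.45

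**3. One mix worked through.** Assume 60% one-type men, split 45/45/10 over mild/moderate/severe, and 40% both-type men, split 35/50/15 before upgrade. Per 100 men after upgrade:

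- Mild: 27, none both-type.
- Moderate: 27 + 14 = 41, of whom 14 both-type.
- Severe: 6 + 20 + 6 = 32, of whom 26 both-type.

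At q = 0.30 and φ = 0.3, response is:

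- Mild: 30.0%.
- Moderate: 0.30 + (14/41) × 0.147 = 35.0%.
- Severe: 0.30 + (26/32) × 0.147 = 41.9%.

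Against mild, the odds ratios are 1.26 and 1.69, although level has no effect. At φ = 0.8 they are 1.07 and 1.17.

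**4. A mix that goes the other way.** Assume one-type men are 15/10/40% of all men and both-type men 35/0/0% before upgrade. Moderate then holds 45%, of whom 35 are both-type. Severe holds 40%, all one-type. At q = 0.30 and φ = 0.3, moderate response is 0.30 + (35/45) × 0.147 = 41.4% and severe is 30.0%. Severe against moderate is (0.300/0.700) ÷ (0.414/0.586) = 0.61.

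**5. Ranges with no true severity effect**, for q = 0.2, 0.3 and 0.4 and severity scored 0/1/2.

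- *Set A*: one-type and both-type splits of 60/35/5 and 50/40/10, 45/45/10 and 35/50/15, or 30/60/10 and 20/65/15, with 20, 40 or 60% both-type men. Odds ratio per level: 1.30–1.63 at φ = 0, 1.12–1.22 at 0.6, 1.03–1.10 at 0.8–0.9.
- *Set B*, heavy in one-type severe men (% of all men, one-type then both-type): 15/10/40 and 35/0/0, 20/20/30 and 25/5/0, or 30/10/25 and 25/10/0. Per level 0.84–1.13 and severe against moderate 0.47–0.86 at φ = 0–0.6; per level 0.97–1.03 at φ = 0.8–0.9.

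**6. Unequal response per component.** At φ = 0 and one-type response of 30%, the second route adds nothing when the both-type rate per component p satisfies 1 − (1 − p)² = 0.30, so p = 1 − √0.70 = 16.3%. At φ = 0.6 the break-even is 22.9%, and at 0.9 it is 28.0%. Below these rates the distortion reverses. If both-type men respond per component at half the one-type rate, Set A gives 0.92–0.98 per level at φ = 0, 0.74–0.88 at 0.6 and 0.65–0.83 at 0.9.

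**7. Masking.** Let per-component response truly fall 40/30/20% by level. The mean odds ratio per level is √[(0.20/0.80) ÷ (0.40/0.60)] = √0.375 = 0.61. On Set A at φ = 0–0.6, with both components at the same level, the planned term shows 0.79 to about 1.15. A model with the level before upgrade and a both-types indicator shows 0.59–0.63. If the second component is always mild, the two models show 0.87–1.43 and 0.66–0.76.

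**The case against.** The strongest reply is that the protocol defines severity as a composite in which coexistence counts as worse, and never says that severity means extent net of the number of components. Asking whether that grade is associated with response is legitimate. This stands: the planned odds ratio is valid for the trial's own label, and the fault arises only when it is read as extent of loss.

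A reader might infer that the plan is biased toward finding that worse loss responds better, or that it will often yield a falsely significant severity effect. The document supports neither. Direction depends on the mix and on response per component, as steps 4 and 6 show. In simulations of 201 men with no severity effect on Set A, p < 0.05 occurred in 22–67% of trials at φ = 0, but in 8–15% at 0.6 and 4–8% at 0.8–0.9. Both components lie on one scalp and are graded from one set of images ("photographs of the scalp were taken from four angles (frontal, vertex, and bilateral sides) for every participant"), so a high correlation is plausible.

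It can also be said that a SAP may add covariates. It may, but the severity rule, the response rule and the named predictors are all in the protocol, so the coupling is already fixed there.

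Finally, the alternative model is not a clean measure of extent. Before upgrade only C3 or U is severe, so the level still mixes extent with pattern type. With no level effect, its level odds ratio of 1.00 holds by construction, because response there depends only on the indicator. These limits are why it belongs beside the planned model and not in its place.

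**Conclusion.** The point holds in a limited form. By the protocol's own rules, men with two routes to response are all moderate or severe, and the named predictors cannot separate that from how advanced the loss is. Neither the size nor the direction of the mixing can be derived from the document. With no true severity effect and equal response per component, the odds ratio per level is about 0.84–1.63 over the assumed mixes. It is close to 1 when the components nearly always improve together, and it can be lower if both-type men respond less per component. This is a modest matter of interpretation for one predictor in a study that calls itself exploratory.

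**What to change.** Keep the planned severity model and report three additions beside it.

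1. A predictor model with the level before upgrade, taken as the higher of the two component levels in the Assessment Criteria list, and an indicator for both types present.
2. Response in one-type and in both-type men, tabulated separately.
3. Component-specific response models, as a sensitivity analysis.

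State that the upgraded label alone will not be used to conclude that extent of loss predicts response.

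**Cost.** No new data are needed, because the endpoint already requires component grades. The standard error of the level term rises by about 8–30% on Set A and 0–14% on Set B. Component models use only men who have that component. Separation stays incomplete when the second component is milder (0.66–0.76 against a true value of about 0.61), and the level before upgrade still carries pattern type. If the SAP already separates the two, nothing needs changing.

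### The primary endpoint is named as change in BASP, but the response rule counts gains in either component only, so in a single arm with no reference rate the responder proportion does not by itself show net change

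*Protocol*

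**What the plan says.** - **Endpoint as named.** Protocol, Design: "The primary endpoint, change in the BASP classification, was assessed by independent, blinded physicians". No direction is attached.
- **Endpoint as operated.** Protocol, Assessment Criteria: "a positive response was defined as an improvement of at least one grade in either the Basic or Specific component of the BASP system", measured from baseline to the day of the last treatment. No BASP category is defined for worsening or for mixed change. The patient questionnaire in the same section does have a deteriorated category.
- **Non-response.** Protocol, Statistical Analysis, describes the ROC outcome as "treatment failure (defined as 'no improvement".
- **Comparator.** Protocol, Design: "a single-arm design was chosen", with the exploratory purpose given as the reason. No reference rate, threshold or before-after test is stated. The named tests (logistic regression, chi-square, trend, ROC) relate response to predictors.
- **Grading.** Protocol, Interventions, Blinding, and Randomization: photographs were "randomly assigned to 2 or 3 independent, blinded physicians", and "The physicians were blinded to the treatment stage (before- or after-treatment" status. Assessment Criteria adds that "disagreements were resolved by a third blinded assessor, with the final outcome determined by a majority decision".
- **Aim and disease.** Protocol, Objective, sets out to evaluate clinical effectiveness and calls the condition progressive.

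**The concern.** Change has two directions and the response rule has one. Two consequences follow from the text. First, a man who gains a grade in one component and loses one in the other is a positive response. Second, a man who only worsens is counted with men who did not change. The Protocol does not say the second in words, but it follows from a binary gain rule whose complement is no improvement.

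This matters because of the design. Graders did not know which photographs came first, so two gradings of an unchanged scalp are exchangeable, and random error yields as many apparent gains as losses. The response rule keeps the gains and is silent on the losses. With no control arm and no reference rate, nothing else in the stated outcome offsets them. The same responder proportion results whether few or many men worsened, and a reader who sees only that proportion cannot tell the two situations apart.

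**Working it through.** The Protocol states no expected response rate and no reader error rate, so there is no figure of its own to reproduce. The only documented number used is N = 201 (Design). Everything else here is an assumption.

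**A. False response when nothing changes.** Let each reader misgrade a photograph set by one grade with probability e in each direction: e = 0.05, 0.10, 0.15, or 10%, 20%, 30% in total. Assume reader errors are independent, that grades are not at the ends of the scale, and that a majority of three decides each grade, with three-way splits taken as correct.

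- Final error each way: g = 3e²(1−e) + e³
- Apparent gain on an unchanged scalp graded twice, one component: f = (1 − [(1−2g)² + 2g²]) / 2
- Two independently graded components, gain in either: F = 1 − (1−f)²
- Two readers disagree on a grade: D = 1 − [(1−2e)² + 2e²]
- If the majority is taken on the response call instead: per-reader false response r = D/2, then m = 3r²(1−r) + r³

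| Reader error | g | f (men of 201) | F (men of 201) | m, one component (men of 201) | D |
|---|---|---|---|---|---|
| 10% | 0.00725 | 1.4% (2.9) | 2.8% (5.7) | 2.4% (4.8) | 18.5% |
| 20% | 0.0280 | 5.4% (10.8) | 10.4% (21.0) | 7.7% (15.5) | 34.0% |
| 30% | 0.0608 | 11.0% (22.2) | 20.9% (41.9) | 13.7% (27.5) | 46.5% |

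The F column supposes that every man has two gradable components. That is an upper-end case, since the Protocol treats two types together as a special situation: "Coexistence of basic and specific types resulted in an upgrade to the next severity level". Under the same model, responders who also worsened in the other component number 2f² × 201 = 0.1, 1.2 and 4.9 men. The mixed group is therefore small when nothing changes; its true size in this trial is unknown.

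**B. Same responder proportion, different net change.** The counts are invented, and no man is mixed. Let 50 of 201 improve: 50/201 = 24.9% responders in both rows. The net difference is d = (improved − worsened)/201, with SE = √[improved + worsened − (improved − worsened)²/201] / 201.

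| Improved | Worsened | d | SE | 95% CI | Exact sign test |
|---|---|---|---|---|---|
| 50 | 20 | +14.9 points | 0.0403 | 7.0 to 22.8 | 50 of 70, p = 0.0004 |
| 50 | 45 | +2.5 points | 0.0485 | −7.0 to 12.0 | 50 of 95, p = 0.68 |

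The stated outcome reads 24.9% in both.

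**The case against.** **A named variable plus a responder cut-off is ordinary practice.** This stands. A responder rate is a legitimate endpoint, the study calls itself exploratory, and the definition need not be withdrawn. What remains is that this rule, with no comparator, does not by itself answer the stated aim of evaluating effectiveness.

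**Tables, intervals and agreement statistics belong in an analysis plan, which is not shown.** This stands in part. Such a plan may already contain a shift table, and nothing in the Protocol says worsened men will go unreported. But the point concerns a definition the Protocol itself fixes: gain in either component, with mixed change counted as success.

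**The no-improvement wording serves only the ROC analysis.** It does define that event. It is also the complement of the response rule, and the regression needs the same two classes.

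**The size is wholly assumed.** This stands. At the low end it is about 3 of 201 men, which is negligible. The independence assumption also matters. Errors shared by all readers of one photograph set would not be voted out: at the extreme, one-component false response is the single-reader r, 0.0925, 0.170 or 0.2325, while readers would never disagree. Errors common to both of a man's photograph sets would cancel. So agreement between readers is useful but can understate error.

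**Stronger readings a reader might infer.** One is that subtracting worsened from improved men gives the number, or a firm range, of true improvers. It does not: that ignores truly changed men who are misgraded, and in a progressive condition worsening mixes error with real progression. Another is that the responder proportion is mostly noise or the treatment ineffective; the Protocol contains no error rate or result from which to say so.

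**Conclusion.** The point holds in a limited form. The endpoint is named as change. The rule counts any-component gains, admits mixed change as response, and leaves worsened men among the non-responders. In a single arm without a reference rate, the resulting proportion contains an unknown amount of grading error in the improving direction and does not by itself show net change.

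Under independent reader errors of 10% to 30%, that amount is about 1.4% to 11.0% with one component. If the majority applies to the response call, it is 2.4% to 13.7%. It reaches about 21% only in the upper-end two-component case. These are illustrations, not estimates for this trial.

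Stage-blinded grading makes the worsened count informative, which is why a net comparison is worth reporting. Its limits are firm: a net near zero would not prove absence of effect, and net change in one arm does not isolate a PRP effect. This is a cheap improvement to reporting and does not invalidate the endpoint.

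**What to change.** 1. Keep the stated response rate and label it as gain of at least one grade in any component.
2. Beside it, from the final blinded grades, report four exclusive categories, each with a 95% CI: improved only (at least one component better, none worse), unchanged, mixed, and worsened only (at least one worse, none better). State how many responders are mixed, so that the response rate and the improved-only count are not confused.
3. Add the improved-only minus worsened-only difference with a 95% CI and an exact sign test, labelled supportive and post hoc.
4. If the separate readings were kept, which the Protocol does not document, report inter-reader agreement per component and note that it can understate error shared between readers.
5. Do not present the responder proportion alone as evidence of effectiveness, and state the limits given in the verdict beside the net difference.

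**Cost.** One extra table and one supportive test, from grades the stated response rule already requires. The agreement statistic depends on whether individual readings survive. The primary definition and the planned association analyses do not change. The downside is a possibly less favourable headline.
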